3.3 Study Drug, Dose, Mode of Administration and Justification

Ketamine is concentrated at a dose of 50mg/ml and will be administered by intramuscular administration in the amount of 60 mg (1.2 ml). This dose follows the FDA-dosing guidelines of a maximum dose of 60 mg per treatment day, with a lifetime maximum of 8 treatments for psychiatric indications. Each study drug administration will be directly observed by the PI. For a 75 kg person, this dose will translate into an effective dose of 0.74 mg/kg based on an intramuscular bioavailability of 93%. While formal dose response studies for depression are lacking, ketamine has been most widely studied for psychiatric indications at 0.5 to 1.0 mg/kg given intravenously. Although there are only a few studies evaluating the use of ketamine in the treatment of substance use disorders, doses in these trials have ranged from 0.5 to 0.8 mg/kg given intravenously or 2 mg/kg given intramuscularly (Jones et al., 2018).

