4.2 Secondary Outcomes

Secondary outcomes will include changes in depression severity (as measured on the Montgomery– Asberg Depression Rating Scale), which will be calculated as a change from baseline to 4-week followup.

Montgomery Asberg Depression Rating Scale (MADRS; Montgomery, 1979). The MADRS is a clinician administered, 10-item questionnaire of depression severity. The total score ranges from 0-60, with scores of 0-6 considered normal (non-depressed), 7-19 indicative of mild depression, 20-34 indicative of moderate depression, and 35-60 indicative of severe depression. Individuals scoring 20 or higher on the MADRS will be included in the study. The MADRS evaluates the following symptoms of depression: 1) clinical appearance of sadness, 2) self-reported sadness, 3) inner tension, 4) reduced sleep, 5) reduced appetite, 6) concentration difficulties, 7) lassitude, 8) inability to feel, 9) pessimistic thought process, and 10) thoughts of suicide. The MADRS has a sensitivity of 94% and a specificity of 83%, has been shown to have high internal consistency, and correlates well with other measures of depression such as the Hamilton Depression Scale.

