10. STUDY DESIGN/METHODS

10.1 Study Overview

This is a double blind, placebo-controlled trial to assess the efficacy and safety of twice weekly intramuscular injections of ketamine in decreasing symptoms of OUD and MDD. Subjects will participate in a baseline visit to complete informed consent as well as complete assessments to evaluate study

eligibility and collect baseline data. Eligible participants will return within one week for the initial ketamine intervention procedure. Immediately prior to the interventional procedure, participants will be guided through a mindfulness-based exercise to facilitate relaxation and reduce anxiety during the intervention. Participants will be subsequently monitored for 120 minutes, during which time they will complete measures assessing their perception of the interventional experience. Participants initially assigned to the placebo group may choose to optionally complete 8 ketamine medication sessions beginning in Study WK #5.

	Groups A & B							
Visit #1: Baselir	ne Assessments		Study WK #0					
Visit #2: 1st Tx	Visit #3: 2nd Tx		Study WK #1					
Visit #4: 1st Tx	Visit #5: 2nd Tx		Study WK #2					
Visit #6: 1st Tx	Visit #7: 2nd Tx		Study WK #3					
Visit #8: 1st Tx	Visit #9: 2nd Tx		Study WK #4					
Visit #10: 1 WK follow-up	Visit #10: 1st KET Tx	Visit #11: 2nd KET Tx	Study WK #5					
Group A (Ketamine)		Placebo): Optional Visits						
Visit #11: 2 WK follow-up	Visit #12: 3rd KET Tx	Visit #13: 4th KET Tx	Study WK #6					
	Visit #14: 5th KET Tx	Visit #15: 6th KET Tx	Study WK #7					
Visit #12: 4 WK follow-up	Visit #16: 7th KET Tx	Visit #17: 8th KET Tx	Study WK #8					
	Visit #18: 1 WK follow-up		Study WK #9					
	Visit #19: 2 WK follow-up	2	Study WK #10					
		2 2	8					
			l					

Visit #20: 4 WK follow-up

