10.3 Schedule of Assessments

The instruments to be used are standardized, have good psychometric properties, and are widely used. The schedule of study assessments is provided in **Table 2**.

Table 2: Schedule of Assessments

Table 2. Schedule of Assessments			TIME POINT										
Instrument Name	Purpose	Wk 0			(Wk6)					Wk 5 (9)	Wk 6 (10)	Wk 8 (12)	
		BL	Tx1	Tx2	Tx3	Tx4	Tx5	Tx6	Tx7	Tx8	1W F/U	2W	4W
Self-Reports and Consent											170		
Informed Consent X													
Demographics Form	Sample characterization	Х											
Concurrent Medications Form	Monitor medications	Х	Х	Х	Х	Х	Х	Х	Х	Х	Х	Х	Х
Treatment Services Tracking Form	Assess treatment engagement	х	Х	Х	Х	Х	Х	х	х	Х	Х	х	х
*Time Line Follow-Back (TLFB)	Primary Outcome: opioid use (amt. and frequency)	х	х	х	х	Х	Х	х	х	х	х	х	х
Beck Depression Inventory-II	Self-reported assessment of depression symptom severity	х	х	х	Х	Х	Х	х	х	х	х	х	х
Visual Analog Scale (VAS)	Measure subjective levels of opioid craving	х	Х	х	х	Х	Х	х	х	х	Х	Х	Х
General Anxiety Disorder (GAD-7)	Self report of anxiety symptom severity	х	Х	х	х	Х	Х	х	х	х	Х	Х	Х
Mystical Experiences Questionnaire	Measure of perceptual experiences		Х	Х	Х	Х	Х	х	х	Х			
Brief Pain Inventory	Measure of pain and quality of life	х		х		Х		х		х			х
University of Rhode Island Change Assessment (URICA)	Measure of motivation for change	х		х		х		х		х			х
Insomnia Severity Index (ISI)	Assess insomnia and sleep quality	х		х		Х		х		х			х
Five Facets of Mindfulness (FFMQ)	Assess aspects of mindfulness related	х		х		Х		х		х			х
PTSD Checklist (PCL-5)	Measure of PTSD symptoms	х		х		Х		х		х			х
Fagerstrom Test of Nicotine Dependence (FTND)	Measure of nicotine dependence	Х		х		Х		Х		х			х
Assessment of the Blind	Participant Perception of Randomization									Х			
Study goals	To characterize goals for treatment	х	х	х	х	Х	х	х	х	х			
	CI	inician	Assess	ments	n	1	1	1		1	n	n	
History and Physical Exam	Eligibility assessment	Х											
Vital Signs Measurement	Obtain readings of blood pressure, pulse, temperature, respirations and pulse oximetry	х	X*	X*	X*	X*	X*	X*	Х*	X*	х	х	х
Modified Observer Alertness/Sedation Scale (MOASS)	Measure of sedation		х	х	х	х	х	х	x	х	х		
Clinical Opioid Withdrawal Scale (COWS)	Clinician assessment of opioid withdrawal symptoms	Х											
*Montgomery-Asberg Depression Rating Scale (MADRS)	Primary Outcome: Clinician assessed measure of depression symptom severity	х		х		х		х		х	х	х	х

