10.5 Method and Administration of Randomization

Randomized permuted blocks will be employed to obtain balanced randomization sequences for the two groups. The PI will be blinded to the randomization sequence and communicated to a designated pharmacist who not involved in clinical management of participants in order to preserve the double-blind design. The randomization assignment of participants will be carried out by this pharmacist

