11.0 SPECIMEN COLLECTION AND BANKING

Data will be in the form of self-reported questionnaires, medical record review (including labs and pertinent medical history for the purpose of eligibility clarification), urine and breath samples, physical exam and electrocardiogram and structured clinical interviews conducted by the PI. This data will be obtained specifically for research purposes. No biologic specimens will be stored for future use. Serum based laboratory tests (complete blood counts, complete metabolic panels) and electrocardiograms will be conducted using MUSC's clinical laboratories with test results entered into the participant's electronic medical record.

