12.0 DATA MANAGEMENT

12.1 Data Analysis Plan

Baseline demographic characteristics will be collected and descriptive statistics will be used to characterize participants. Data will be collected and managed using the secure REDCap (Research Electronic Data Capture) database. Descriptive statistics for primary outcomes will include 1) the percentage of individuals completing informed consent out of the number of individuals eligible on the

initial screening and 2) the percentage of individuals that complete informed consent which complete the full protocol. Other descriptive statistics for the sample population will be analyzed, and baseline characteristics that are found to be significantly associated with other outcome measures will be included as covariates. Spaghetti plots will be produced to guide modeling outcomes as a function of time. All analyses will be conducted based on intention to treat. Subjects assigned to Group B (placebo) who complete Study Wk4 (at which time main outcomes are assessed), may choose to receive 8 ketamine treatments before completing follow-up visits. To preserve study blinding, subjects who are among the final 6 subjects being enrolled will not be unblinded until primary outcomes are assessed for all 30 subjects.

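### Arms disclosed at Wk 5 for the first 24 participants let an observer guess, and sometimes know, a later block-mate's arm before the Wk 4 MADRS (low severity, optional fix)

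*Combined protocol and SAP*

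**What the plan says.** - **Hold on unblinding (12.1).** To protect the blind, "subjects who are among the final 6 subjects being enrolled will not be unblinded until primary outcomes are assessed for all 30 subjects". Nothing comparable covers the first 24.
- **Optional ketamine (10.1).** "Participants initially assigned to the placebo group may choose to optionally complete 8 ketamine medication sessions beginning in Study WK #5". Participants in the ketamine arm go to follow-up visits instead.
- **Allocation (10.5).** "Randomized permuted blocks will be employed to obtain balanced randomization sequences for the two groups". Block size, whether it varies, and who knows it are not stated. The same section says "The PI will be blinded to the randomization sequence" and gives assignment to a pharmacist outside clinical management.
- **Who sees dosing (3.3).** "Each study drug administration will be directly observed by the PI".
- **The outcome exposed.** Under 4.2, "Secondary outcomes will include changes in depression severity", measured by the MADRS. The schedule in 10.3 describes the scale as a "Clinician assessed measure of depression symptom severity", and 12.3 bases the power calculation on it. No rater is named. Section 11 lists "structured clinical interviews conducted by the PI" among the data sources.

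**The concern.** The hold for the final 6 shows that the authors saw the problem: a disclosed arm can inform judgement about someone still under assessment. The same reasoning applies to earlier blocks, where the plan is silent. Within a permuted block the arms must balance, so each opened code shifts the odds for the remaining members, and enough codes from one arm settle them.

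At stake is the blind on a clinician-rated scale in a trial with 15 per arm. Section 10.5 keeps the sequence from the PI, but the Wk 5 offer can open completed parts of it to the PI during accrual. The exposure is mainly at rating rather than at enrolment. For block sizes 2 to 6, the expected number of arms fixed before the person enrols is 0 to 0.4 with regular arrivals and about 1.2 with Poisson arrivals.

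**Working it through.** **Inputs from the plan.** 30 participants, 15 per arm, 2 per month for 15 months, dropout up to 20% (12.3); 60% expected to complete (12.2); 24 = 30 − 6 outside the hold (12.1); optional ketamine from Wk 5 (10.1); perceptual effects expected in 42% on ketamine (15.3). **Assumed:** block size, and that each non-held arm becomes known at about Wk 5.

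**The plan's own figures.** Accrual: 2 × 15 = 30, as stated. Detectable MADRS difference: (1.96 + 0.84) × 15.8 × √(2/15 × 0.798) = 14.4, as stated, where 0.798 is the mean entry of the 7 × 7 AR(1) matrix at 0.9. Neither is disputed.

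**Timing.** Mean spacing is (52/12)/2 = 2.17 weeks. A code opens 4 to 5 weeks after first dose. The next participant's last Wk 4 visit falls at about 2.17 + 3.5 = 5.7 weeks on that clock. At even accrual, earlier codes are therefore open by then, with about 0.7 week to spare in the later case.

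**Certain cases, block size fixed and known.** In a block of 2b, a participant's arm is settled only if all b members of the opposite arm came earlier and their codes are open. The chance of coming last among those b + 1 people is 1/(b + 1). If a share d of codes stays closed, and only rated participants count, the expected number among the first 24 is 24/(b + 1) × (1 − d)^(b + 1).

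| Block size | d = 0 | d = 0.2 | d = 0.4 |
|---|---|---|---|
| 2 | 12.0 | 7.7 | 4.3 |
| 4 | 8.0 | 4.1 | 1.7 |
| 6 | 6.0 | 2.5 | 0.8 |

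Here d = 0.2 is the dropout in 12.3. d = 0.4 is the non-completion in 12.2, a bounding case because some non-completers may reach Wk 4.

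**Sensitivity to arrivals, all codes open, blocks of 4 and 6.** Poisson arrivals give 6.8 and 5.1. Same-day pairs give 4.0 and 3.2. If each code opens only after the next participant's Wk 4 rating, both become 2.0 (and 0 for blocks of 2).

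**Size fixed but undisclosed.** Let the observer entertain every even size from 2 to 10, discard sizes that the opened codes contradict, and count a case only if all remaining sizes force the same arm. By simulation with all codes open this gives about 0.6 (true size 4) and 2 (true size 6). The result depends on that list: an observer who thinks only 4 or 6 plausible reaches about 4.7 and 5.2.

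**Size concealed and not inferable.** 0.

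**Best-guess accuracy, all earlier codes open.** Averaging the chance of a correct guess over block positions:
- Blocks of 4: (1/2 + 2/3 + 2/3 + 1)/4 = 71%.
- Blocks of 6: (0.5 + 0.6 + 0.6 + 0.7 + 0.7 + 1)/6 = 68%.

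**The final 6.** For blocks of 2, 4 or 6, participant 24 ends a block, so earlier codes do not reach participants 25 to 30.

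**With varied blocks.** Sizes 4, 4, 6, 8 and 8 in random order, judged by someone who knows the set but not the order: by simulation about 0.8, 0.2 and 0.02 certain cases among the first 24 at d = 0, 0.2 and 0.4, with best-guess accuracy about 67%.

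**The case against.** - **Silence on block size is not proof of a fixed, known size.** This stands. A size printed in the PI's own protocol would weaken concealment, so leaving it out fits good practice too. A reader might infer that a third of the first 24 (8 of 24) will have a known arm. The documents do not support that, because it needs a fixed, known size, every code open and even accrual.
- **The rater is not identified.** This stands. A reader might infer that the PI rates the MADRS. The phrase in section 11 fits the Mini International Neuropsychiatric Interview in the schedule at least as well.
- **Disclosure of the first 24 is itself inferred.** True, no sentence states it. But a placebo-only offer and a hold limited to 6 leave little other reading.
- **Functional unblinding is already large.** This stands. If 42% on ketamine and, by assumption, none on saline have perceptual effects, guessing from these alone is right in 0.5 × 0.42 + 0.5 × 1 = 71%. Combined with block information, assuming independence, the figure is 79% or 81% with fixed blocks of 6 or 4, and 78% with the varied blocks. Varying block size therefore gains only 1 to 3 points.
- **A rater can be swayed by a good guess as well as by certainty.** This stands too. Varied blocks cut certain deductions sharply only against a fixed, known size, and barely move the guess.

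**Conclusion.** The point holds as a minor weakness. A stated rule, the hold limited to the final 6, combined with the placebo-only offer, works against the PI blinding set out in 10.5. Open codes would allow about 68 to 71% best-guess accuracy with fixed blocks of 6 or 4. The expected number of certain cases among the first 24 runs from 0 (size concealed and not inferable), through about 0.6 to 2 (fixed at 4 or 6, undisclosed, even sizes 2 to 10 entertained), to 6 to 8, or 12 for blocks of 2 (fixed and known). Closed codes lower every figure above 0.

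This does not show that the MADRS comparison is biased: the size of any effect is unknown, and saline control already leaks information. The feasibility primaries are untouched and efficacy is assessed only preliminarily. Severity is low and the change optional. It is still worth making, because the MADRS is the outcome the trial is powered on and the change costs little.

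**What to change.** 1. **Section 10.5:** state that block sizes vary at random and are known only to the pharmacist and the statistician. For example, 4 + 4 + 6 + 8 + 8 = 30 in random order keeps 15:15.
2. **Section 12.1:** state that codes opened at Wk 5, and attendance at the optional ketamine course, are not shared with whichever existing qualified team member rates the MADRS in participants not yet past Wk 4.

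The second step does most of the work, and it helps only if that rater is not the PI who observes dosing. Naming the rater would settle this.

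The cost is one sentence in each section and minor rating logistics. The possible mid-trial imbalance is slightly larger: up to 4 within a block of 8, against 2 or 3 for blocks of 4 or 6. No extra staff, participants or visits are needed, and the optional course is not delayed. Closing all codes until the last Wk 4 assessment would bring the certain cases to 0, but it would delay that course for early placebo participants and is not required.

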12.2 Hypotheses for Analyses

Feasibility Hypothesis: From the cohort of individuals completing the initial prescreening assessment, a 75% study enrollment rate will be deemed feasible. Therefore, we anticipate that 40 individuals will be needed to complete prescreening so that 30 participants will enroll in the study. Of the individuals enrolling in the study, we anticipate 60% of participants will *complete* the study protocol. *Completion* is defined for the study purposes as completing at least 75% of the study visits.

Hypothesis 1: Ketamine will result in significantly greater reduction in depression symptoms as compared to placebo at one-month. To test this hypothesis, we will employ repeated measures ANOVA using linear mixed models approach to assess reduction on the total score of the MADRS.

Hypothesis 2: Ketamine will result in significantly greater reduction in frequency of opioid use as compared to placebo at one-month. To test this hypothesis, we will treat the percent days using opioids (TLFB) as a continuous variable and analyze using linear mixed models approach. Abstinence at one-week (on UDS) will be compared by intervention groups using logistical regression analyses. An arcsine square root or logit transformation may be considered to stabilize variance of the proportions.

Hypothesis 3: Response to ketamine will be influenced by changes in motivation to quit (URICA) and qualities of psychoactive perceptual experience (HMS). To test this hypothesis, we will employ repeated measures ANOVA using linear mixed models approach.

Alternate Approaches: Diagnostics of the residuals will be performed to test the assumptions of the analysis. If the assumptions are found to be inadequate, alternative methods of analysis (e.g. ordinal logistic regression or Poisson regression) will be considered.

The primary dependent variables in all three analyses will be intervention group (ketamine or placebo), time (number of days), and the interaction between the two. Main hypothesis of interest will be the interaction and the post-hoc comparison at the one month after the first intervention. We anticipate the study population to include participants that are currently on antidepressants as well as those that are not. We considered stratifying randomization by this variable, however since the proporption of participants on antidepressants at baseline is expected to be small, this will be considered as an independent variable in the statistical analysis. To account for within subject correlations, several structures, such as spatial autocorrelation (to accommodate unequal time points), and AR(1) symmetry, will be examined. Diagnostics will be considered. An arcsine square root transformation may be considered to stabilize variance of the proportions. In all of the analyses, covariates will be considered to examine mediations. In a secondary analysis based on the spaghetti plots, we will consider linear and non-linear models of outcomes as a function of time. Specifically, over the 8-week follow-up period, we will examine if there exists a threshold point in time where the effect of ketamine plateaus. To achieve this, treating the joint-point as unknown, we will fit segmented regression models using non-linear mixed models.

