4.0 STUDY ENDPOINTS

4.1 Primary Outcomes

Primary outcomes will be 1) the percentage of individuals completing informed consent out of the number of individuals eligible on the initial screening and 2) the percentage of individuals that complete informed consent which complete the full protocol.

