10.2 Duration of Intervention and Study

Participants will complete a total of 12-20 study visits (including baseline assessment) as shown in **Figure 1**. Intervention visits will occur over a 4-8 week period, with three follow-up visits completed over the subsequent four weeks.

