12.3 Justification of Sample Size

PROTOCOL TITLE: Ketamine for the Treatment of Opioid Use and Depression Version Date: December 20, 2021

For a 75% anticipated enrollment rate from the initial prescreened sample of 40 individuals, feasibility can be estimated within a margin of error of 14% with 95% confidence. Similarly, assuming a 60% rate of study enrollment of eligible participants, with a sample size of 30 we can estimate feasibility within a 17% margin of error with a 95% confidence interval. This study is powered to estimate the effects of ketamine on significant reduction in MADRS symptoms at the end of one month (see Hypothesis 1). Over the course of a two-year study, we estimate that we will be able to recruit 15 patients in each of the two intervention arms (2/month over 15 months). At 80% power, this sample size will allow us to detect a minimum difference in MADRS scores of 14.4 at one month between the ketamine and the placebo groups in a study design with 7 repeated measurements having a AR(1) correlation of 0.9, and a standard deviation of 15.8, with a significance level of 0.050 (Singh et al., 2016; Niciu et al., 2014). While we will examine changes in depression severity as a continuous variable, we will also examine other clinically accepted changes in depression severity such as response (defined as a 50% reduction in symptom severity from baseline) and remission (defined as below the threshold for mild depression which is a score of 6 on the MADRS). Baseline averages for the MADRS scores for this population will be assumed to be 34 (Niciu et al., 2014; Han et al., 2016; Singh et al., 2016). The minimum difference in MADRS of 14.4 is anticipated to be approximately 50% of the baseline measurements. Although there is limited information on the effectiveness of ketamine in the treatment of addiction, a sample of 30 subjects (15 in each arm) will provide adequate power to detect an 22% difference between the two groups in the percent of days abstinent from opioid use using the same longitudinal design as described above with 7 time points (Hypothesis 2). For this calculation, we assumed an AR(1) correlation of 0.9 and a standard deviation of 25% at a significance level of 0.05; an arcsine transformation was used for variance stabilization. Over the 8-week follow-up period, we will examine if there exists a threshold point in time where the effect of ketamine plateaus. To achieve this, we will use a segmented regression analysis using non-linear mixed models. We will take all efforts to keep dropouts to a minimum. However, our past experience suggests the rates of dropout are up to 20%. This could reduce the sample size per group to 12 and 12. The corresponding differences we could detect would be a minimum MADRS score difference of 16.1 and a 26% difference between groups in terms of the percent of days abstinent from opioid use. No interim analyses are planned.

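### Does the 75% completion rule fail because some placebo participants can have 20 study visits rather than 12?

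*Combined protocol and SAP*

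**What the plan says.** Section 4.1 names two primary outcomes, both about feasibility. The second is "the percentage of individuals that complete informed consent which complete the full protocol". Section 12.2 softens the word full: completion "is defined for the study purposes as completing at least 75% of the study visits". The same paragraph gives the forecast: "Of the individuals enrolling in the study, we anticipate 60% of participants will" complete.

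The number of visits varies. Section 10.2 states: "Participants will complete a total of 12-20 study visits (including baseline assessment". The spread comes from section 10.1: "Participants initially assigned to the placebo group may choose to optionally complete 8 ketamine medication sessions beginning in Study WK #5". Section 12.1 adds that placebo participants who complete week 4 "may choose to receive 8 ketamine treatments before completing follow-up visits", so their three follow-ups come after the extra sessions. It also says that participants among the last six enrolled "will not be unblinded until primary outcomes are assessed for all 30 subjects".

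Section 12.3 gives a 17% margin of error for a 60% rate with 30 participants, but introduces it as "assuming a 60% rate of study enrollment of eligible participants".

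**The concern.** The rule is a percentage of an unnamed total. Section 10.2 includes the optional sessions in its count of study visits, and section 12.2 uses the same term in the completion rule. Read literally, a placebo participant who takes the option is measured against 20 visits and everyone else against 12. The bar would then depend on arm and on a choice made after randomisation.

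A primary outcome would be at stake. One set of attendance data would give two completion rates, and the base could be picked once attendance is known. There is also a possible circularity. If the outcomes awaited before the last six are unblinded include completion on a 20-visit base, that completion cannot be known beforehand, because only participants known to be on placebo are offered the extra sessions.

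**Working it through.** **1. Visit counts (schedule in section 10.1).**
- Without the option: 1 baseline + 8 treatment + 3 follow-up = 12.
- With the option: 1 + 8 + 8 + 3 = 20.

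Both ends of the range in section 10.2 are reproduced.

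**2. Thresholds.** 0.75 × 12 = 9 visits; 0.75 × 20 = 15 visits.

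**3. Who is affected.** The ketamine arm and placebo participants who decline have 12 visits on any reading. Only placebo participants who accept can be reclassified: at most 15 of 30 (15 per arm, section 12.3).

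**4. How a record changes class.** Someone who attends Visits 1 to 9 has 9/12 = 75% before any optional session. On a base of 20 that person needs 15 − 9 = 6 of the remaining 20 − 9 = 11 visits. Stopping at 9 to 14 visits gives 9/20 = 45% to 14/20 = 70%: a non-completer on 20 visits, a completer on 12.

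**5. Size.** Take 30 as the number of people, as section 12.3 does.
- One participant: 1/30 = 3.3 points.
- Forecast: 0.60 × 30 = 18 completers.
- Margin of error: 1.96 × √(0.6 × 0.4 / 30) = 17.5 points, against 17% stated.

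| Reclassified | Completion rate | Shift (points) |
|---|---|---|
| 0 | 18/30 = 60.0% | 0 |
| 2 | 16/30 = 53.3% | 6.7 |
| 5 | 13/30 = 43.3% | 16.7 |
| 6 | 12/30 = 40.0% | 20.0 |

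The documents give no uptake rate and no stopping rate for the optional phase, so the row that applies is an assumption. As one illustration, suppose 9 of the 18 completers are placebo participants who attended Visits 1 to 9 and all accept. Borrowing the 20% dropout rate of section 12.3 gives 0.20 × 9 = 1.8, about 2 people. The arithmetic ceiling of 15 people (50 points) requires every placebo participant to be a completer on 12 visits, accept the option and then fall short of 15 of 20.

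**6. Which base the text supports.**
- Section 1.3 describes treatment twice weekly for four weeks, with measurement up to 8 weeks after the first treatment.
- Aim 1 in section 1.4 concerns completing the treatment protocol.
- Section 10.6 describes four weeks of treatment and four further weeks of follow-up.
- Section 10.1 makes the extra sessions a choice. Declining a choice is not ordinarily a failure to complete a protocol.
- Table 2 in section 10.3 has twelve time-point columns: baseline, eight treatments and three follow-ups. The follow-ups carry second week numbers in brackets (9, 10, 12), so they can be identified by type even when they move.

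On that base the optional sessions enter neither numerator nor denominator. The option cannot then change the status of anyone who attended all of Visits 1 to 9.

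**7. The unblinding sentence.** The sentence just before it in section 12.1 places the main outcomes at week 4. Section 1.3 puts primary outcomes at one month after the first treatment, and Table 2 labels MADRS and the Timeline Followback as primary. In that setting the sentence most naturally means the one-month clinical outcomes, and nothing is circular.

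**The case for a change.** The strongest case for a change is that the plan never says the optional sessions are excluded, and section 10.2 counts them under the very term used in the completion rule. Feasibility is the trial's first aim, so its completion figure should not rest on a convention. Six reclassified participants would move it by more than the stated margin of error. Visit numbers do not settle the matter either: Visits 10 to 12 are follow-ups in the ketamine arm but ketamine sessions for those who take the option, whose follow-ups become Visits 18 to 20. Naming the visits would cost a few sentences.

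The ambiguity in the wording is real, and that much stands. One small asymmetry also survives on a base of 12: a participant who takes the option and still needs follow-ups to reach 9 must stay to weeks 9 to 12 rather than weeks 5 to 8.

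The rest is weaker. Unequal thresholds would bias a comparison of completion between arms, but none is planned; sections 4.1 and 12.1 report one pooled percentage. Section 12.2 attaches the word feasible only to the 75% enrollment rate, and the 60% is a forecast. Setting a definitional shift against a sampling margin does not show that the shift will occur. A shift in the other direction, such as 6 of Visits 1 to 9, all 8 optional sessions and 1 follow-up (15/20 = 75%, but 7/12 = 58.3%), requires that someone who missed three of the first nine visits still counts as having completed week 4.

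**Conclusion.** No change is called for. The denominator is a missing detail that analysts would sensibly fill with the 12 non-optional visits: baseline, eight blinded treatment visits and three follow-ups whenever they fall. The completion bar is then 9 of 12 for everyone, and no stated rule gives a wrong result. The size of the ambiguity is 3.3 points per reclassified participant, for somewhere between 0 and 15 people. The actual number cannot be derived from the documents, and no test or success criterion depends on it.

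The 60% label in section 12.3 is clerical. The sentence before it already covers enrollment (75% of 40 prescreened). The base of 30 is the enrolled sample, and 60% is the completion forecast of section 12.2, so the intended meaning is plain. The 20% dropout allowance in section 12.3 serves the power calculation and does not conflict with 60% completion.

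This conclusion assumes that optional sessions lie outside the required protocol, which the text supports without saying so, and that completion stays a pooled descriptive figure. If completion were to be compared between arms or given a pass mark, the visit base would need to be fixed first.
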